Draft 1.1	February 6, 2018	Document creation by Eurofins Optimed
Draft 1.2	May 30, 2018	Integration of Pharmacokinetic analysis by PhinC development
Draft 2	October 24, 2018	Document sent to sponsor for reading
Draft 3	April 04, 2019	Integration of sponsor comments
Version 1.0	April 05, 2019	Final version

LIST OF ABBREVIATIONS

General terms

a.m.	Ante meridian
EOS	End Of Study Visit
ICH	International Conference on Harmonization
IMP	Investigational Medicinal Product
MAD	Multiple administration dose
MedDRA	Medical Dictionary for Regulatory Activities
NTEAE	Non-Treatment Emergent Adverse Event
SAD	Single administration dose

Safety & medical

AE	Adverse Event
BP	Blood pressure
bpm	beats per minute
BW	Body Weight
ECG	Electrocardiogram
HR	Heart Rate
IV	Intravenous
SAE	Serious Adverse Event
SBP	Systolic Blood Pressure
TEAE	Treatment Emergent Adverse Event

Biologics

ALT	Alanine Leucine Transferase
AST	Alanine serine transferase
CHC	Chronic viral hepatitis C
CPK	Creatine phosphokinase
GGT	Gamma Glutamy1 Transferase
HBs	Hepatitis B surface antigen
HCV	Hepatitis C virus
HIV	Human Immunodeficiency Virus
HIV1	Human Immunodeficiency Virus type 1
HIV2	Human Immunodeficiency Virus type 2
MCH	Mean Corpuscular Hemoglobin
MCHC	Mean Corpuscular Hemoglobin Concentration
PNM	Polimorphonuclear leukocytes
ROS	Reactive Oxygen Species
WBC	White Blood Cells

Bioanalysis

ALQ	Above limit of quantification
LOQ	Limit of quantification
ULOQ	Upper limit of quantification

Pharmacokinetics

A_{e,ur}	Amount excreted in urine
A_{e,f}	Amount excreted in feces

AUC	Area under the plasma concentration-time curve
AUC_{0-t}	Area under the plasma concentration-time curve from time zero to the final time point
AUC_{0-∞}	Area under the plasma concentration-time curve from time zero to infinity
AUC₀₋₂₄	Area under the plasma concentration-time curve from time zero to 24 hours post-dosing
CL/F	Apparent clearance
CL_R	Renal clearance
C_{max}	Maximum plasma concentration
f_{e,ur}	Percentage of the dose excreted in the urine
f_{e,f}	Percentage of the dose excreted in the feces
PK	Pharmacokinetic(s)
t_{1/2}	Terminal half-life
t_{last}	Time of last measurable concentration
t_{max}	Time of maximum plasma concentration
Vz/F	Apparent volume of distribution
λ_z	Terminal phase rate constant

Statistics

CI	Confidence Interval
GM	Geometric mean
Min	Minimum
Max	Maximum
N	Number
PDS	Pharmacodynamic set
PKS	Pharmacokinetic set
RS	Randomized set
SD	Standard Deviation
SEM	Standard Error of the Mean
SS	Safety set

1 INTRODUCTION

In accordance with the main characteristics of the protocol, the Statistical Analysis Plan (SAP) details that the scheduled analyses are to be performed in order to evaluate the tolerability and safety of ascending single and repeated doses of DF2755A in healthy adult male and female volunteers.

Study design

The study is a phase I, single center, double-blind, placebo controlled, randomized, ascending single and repeated doses study in healthy male and female volunteers.

The design consists of a double blind comparison of the test compound versus placebo in which the dose is increased in successive treatment periods.

The Multiple Ascending Dose (MAD) will be initiated only after the authorization, from ANSM of a substantial amendment that will be presented in order to notify the results of Single Ascending Dose (SAD) part of the study. Besides in order to decide to move forward from SAD to MAD, the pharmacokinetic data for all doses administered during SAD will be evaluated (i.e. plasma: quantitative determination of DF2755A bound and unbound; qualitative and preliminary quantitative determination of known metabolites; urine and faeces: qualitative and quantitative determination of parent compound and qualitative and preliminary quantitative investigation of known metabolites).

Dose will be escalated in order to achieve enough safety information on an interval of doses possibly encompassing both the effective dose and the maximum tolerated dose (defined as the highest dose devoid of any clinical signs/symptoms).

Part A: Single doses of 50 mg oad, 150 mg oad, 450 mg oad or 700 mg oad of DF2755A are planned to be tested in healthy male and female volunteers.

Objectives of the study

Primary objectives

- To evaluate the tolerability and safety of ascending single and repeated doses of DF2755A in healthy adult male and female volunteers.

Secondary objectives

- To determine the pharmacokinetics parameters of DF2755A.
- To establish a dose concentration-response relationship over a wide range of doses in order to select a narrower range of dose and dosing regimen to be subsequently studied in patients after single and multiple administration.
- To evaluate the effect of ascending single and repeated doses on the pharmacodynamics parameters.
- To compare metabolites pathway in Human with the one observed in animals.

Criteria for evaluation

Primary evaluation criteria:

AE, vital signs, 12-lead ECG, physical examination, laboratory exams.

Secondary evaluation criteria:

Pharmacokinetics: measurement of pharmacokinetics parameters: C_{max} , t_{max} , λ_z , $t_{1/2}$, AUC_{0-t} , $AUC_{0-\infty}$, V_z/F , CL/F , $A_{e,ur}$, $A_{e,f}$, $f_{e,f}$, $f_{e,ur}$, CL_R , parent:metabolite(s) ratio.

Pharmacodynamics: measurement of leukocyte markers: CD11b, CD18 and reactive oxygen species (ROS).

Study schedule

Table 1: STUDY FLOW CHART – PART A: from cohort 1 to cohort 4

Visit/Period	Screening	Inclusion	Treatment period	End of study visit
Day	D-21 to D-2	D-1	D2	D3
				D4
Informed consent	X			
Inclusion/Exclusion criteria ¹	X	X		
Previous Medical / Surgical History	X			
Prior/concomitant medications	X	X		
Physical/Medical examinations	X	X		
Body weight, height	X	X		
Haematology	X	X		
Hemostasis	X	X		
Biochemistry	X	X		
Urinalysis	X	X		
Serology	X			
Urine test for drug abuse	X	X		
Alcohol breath test	X	X		
Admission	X			
Discharge			X	
Randomization	X			
Study Drug / Placebo Administration ²		X		
Vital signs : Blood pressure / Heart rate	X	X	X	X
/ Oral body temperature				
12-lead ECG recording ³	X	X	X	X
Blood sample for Pharmacokinetics		X	X	X
Blood sample for Pharmacodynamic ⁵		X	X	X ⁶
Urine collection		X	X	X
Faeces collection		X	X	X
AE collection ⁴				↗

¹Confirmation of the Inclusion/exclusion criteria prior to randomization number assignment;

²Dose: Cohort 1, 2; 3 & 4; Single dose in the morning; All subjects will be in fasting conditions from the evening before (at least 10 h, overnight);

³Safety ECG;

⁴All AEs will be reported

⁵Starting only from the second ascending dose;

⁶T48h or T72h: time will be determined after results of the first dose administered.

When ECG, vital signs and PK are required at the same time, this specific order will be followed: vital signs first, then ECG and blood sample for PK at the end.

Table 2: DETAILED FLOW CHART – PART A

Visit/Period	Inclusion	Treatment period														D1		D2		D3		D4	
		D-1		D1		D2		D3		D4													
Day	D-1	Pre	T0	T0.5	T1	T2	T3	T4	T5	T6	T7	T8	T9	T10	T12	T16	T24	T36	T40	T48	T60	T72	
Theoretical time (h)																							
Inclusion/Exclusion criteria	X																						
Prior/concomitant medications																							
Physical/Medical examinations	X																					X	
Body weight; height	X																				X	X	
Haematology	X																				X	X	
Hemostasis	X																				X	X	
Biochemistry	X																				X	X	
Urinalysis	X																				X	X	
Urine test for drug abuse	X																						
Alcohol breath test	X																						
Admission	X																						
Discharge																						X	
Randomization		X																					
Study Drug Administration		X																					
Blood pressure / Heart rate / Oral Body Temperature	X	X				X	X	X	X	X	X	X	X	X	X	X	X	X	X	X	X	X	
12-lead ECG recording	X	X				X	X	X	X	X	X	X	X	X	X	X	X	X	X	X	X	X	
Blood sample for Pharmacokinetics						X	X	X	X	X	X	X	X	X	X	X	X	X	X	X	X	X	
Blood sample for Pharmacodynamics						X															X ¹		
Urine collection	X																				X ¹		
Faeces collection		X																			X	X	
AE collection																							

¹T48h or T72h: time will be determined after results of the first dose administered

2 DEFINITION OF POPULATIONS AND STUDY TREATMENTS

2.1 Randomization

The randomization list was prepared to permit that one of the two first subjects treated per each cohort, received a placebo.

The treatments were allocated at D1 for both parts.

2.2 Justification for number of subjects

No formal sample size calculation was made. The subjects treated with test product and the subjects treated with placebo are considered sufficient to detect drug effects and determine pharmacokinetic parameters before escalating to the next dose level.

SAD cohorts: Thirty -two (32) healthy volunteers (HV) + 4 reserve subjects (total 36) will be enrolled to have 4 groups. Three groups of eight (8) male subjects and one group of 4 M +4 F.

MAD cohorts: MAD cohorts: Thirty -six (36) healthy volunteers (HV) + 4 reserve subjects (total 40) will be enrolled to have 3 groups. Two groups of twelve (12) male subjects and group of 6M+6 F.

2.3 Screening, inclusion and randomization numbers

The screening number was S and 3 digits, for example: S003. It was a chronological number. The screening number was used throughout the screening period, until subjects are randomized.

The inclusion number was composed of 7 digits, 3 for the number of centre (001) and 4 for the inclusion number: from 1001 to 1032 for part A. It will be a chronological number.

The randomization number was the same as the inclusion number and the treatment number.

2.4 Analysis populations

The Randomized set (RS) will be defined as all randomized subjects.

The Safety set (SS) will be defined as all included subjects having taken at least one dose of study drug.

The pharmacokinetic set (PKS) will be defined as all the included subjects who have taken at least one dose of study drug without major protocol deviations affecting pharmacokinetics and with available data.

The pharmacodynamic set (PDS) will be defined as all the included subjects who have taken at least one dose of study drug without major protocol deviations affecting pharmacodynamics and with available data.

2.5 Study treatment

Name of the compound:	DF2755A
Pharmaceutical form:	Capsules of 50 mg, and 200 mg
Dose per administration:	Part A: 50 mg oad, 150 mg oad, 450 mg oad or 700 mg oad
Timing for administration:	Part A: Single oral dose administration on D1 according to the randomization. The administration will take place at around 8:00 a.m with 200 ml of tap water, in sitting position, in fasting conditions.
Name of the compound:	Placebo
Pharmaceutical form:	Matching capsule
Dose per administration:	NA
Timing for administration:	Part A: Single oral dose administration on D1 according to the randomization. The administration will take place at around 8:00 a.m with 200 ml of tap water, in sitting position, in fasting conditions.

3 STATISTICAL ELEMENTS

The statistical analysis performed by EUROFINS OPTIMED pertains to description at baseline, conduct of the study and safety analysis with statistical software SAS (version 9.4).

The pharmacokinetic statistical analysis will be performed by PhinC Development.

The Correlation analysis between pharmacokinetic and pharmacodynamic parameters will be performed by EUROFINS OPTIMED.

Interim analysis: For each part of the study, an interim PK analysis on DF2577Y (the acid form of DF2755A) and its metabolites (if any) will be performed after completion of each dose level. This analysis will be done on anonymized data provided by the bioanalytical center to prevent any violation of the double blind condition of the study.

Final PK analysis will be performed using final validated bioanalytical data and actual PK blood sampling times.

For safety parameters (laboratory safety parameters, vital signs, ECG), in case of repeat assessments, the last assessment prior to the administration of the study treatment and the first assessment after the administration will be used for descriptive statistics. All assessments, including the repeat assessment will be included in the data listings and will be flagged accordingly.

3.1 Statistical methods

The methodology presented in this statistical analysis plan takes into account methods planned in the protocol.

3.2 Descriptive statistics

At least the following descriptive statistics will be reported:

- *Continuous variables*: Number of observations (N), mean, standard deviation (SD), standard error of the mean (SEM) minimum (Min), median and maximum (Max).
- *Categorical variables*: Frequency (n) and percentage (%).

3.3 Statistical tests

Safety analysis

The safety analysis will be descriptive.

Pharmacokinetic analysis

In the first time, pharmacokinetic analysis will be performed for the single ascending dose part (part A).

- Descriptive statistics for drug concentrations:

For descriptive statistics, individual bound and unbound plasma concentrations of DF 2577Y and its related metabolites will be presented by dose level and nominal time points, when applicable.

Descriptive statistics for the plasma concentrations will be presented as number of available data (N), mean, standard deviation (SD) and will be calculated if at least 2/3 of the plasma values per time-point are above LOQ. For descriptive statistics calculations, concentrations below LOQ will be set to zero (0) if they are reported before the first quantifiable sample or considered as missing data if they are reported after the first quantifiable data.

Individual measured plasma concentration vs. actual time curve will be produced in graphic for each compound (parent and metabolites), for each subject, for each dose level on both linear/linear and log/linear scales where applicable. Similarly, mean plasma concentration vs. time curves will also be produced for each dose level.

- Derivation of PK parameters and descriptive statistics for PK parameters:

For the calculation of the PK parameters from plasma concentrations of DF2755Y and its metabolites (if any) using NCA approach the following rules will be applied:

- All the plasma concentrations validated by the bioanalytical laboratory and provided to the pharmacokineticist will be used for the PK analysis.
- The actual blood sampling time points related to the preceding administration will be used.
- At time points in the lag-time between time zero and the first concentration equal or above the limit of quantification (LOQ), concentrations below LOQ will be set to zero (0). Concentrations below LOQ between 2 concentrations equal or above LOQ will be considered as missing data. Trailing concentrations below LOQ will not be used in calculations.
- For plasma concentration above the upper limit of quantification (ULOQ) and reported as above the limit of quantification (ALQ) in the final plasma concentration tables, ALQ will be replaced by the first measurement for the PK analysis.
- Not reported concentration (NR) will be excluded from the PK analysis.
- Pre-dose concentration is less than or equal to 5% of C_{max} value in a PK profile, the subject's data can be included in all PK measurements and calculations without any adjustments. If the pre-dose value is greater than 5% of C_{max} , the subject will be dropped from all statistical evaluations (applicable only at the predose on day 1).

The urinary PK parameters will be calculated from the urine concentrations, the volume of urine collected in each collection interval sample and the start and stop time of each interval.

The fecal PK parameters will be calculated from the fecal concentrations, the weight of feces collected in each collection interval sample and the start and stop time of each interval.

The following PK parameters of DF 2577Y bound and unbound (or related metabolites) will be derived from for each subject:

- **C_{max}** The observed maximum plasma concentration of DF 2577Y (or metabolites) measured in a subject after dosing identified by inspection of the plasma drug concentration *versus* (vs.) time data.
- **t_{max}** The time at which C_{max} was apparent, identified by inspection of the plasma drug concentration vs. time data.
- **λ_z** The terminal plasma elimination rate-constant will be estimated from log-linear regression analysis of the terminal phase of the plasma concentration vs. time profile. For the slope of the terminal elimination phase to be accepted as reliable, the following criteria will be imposed:
 - a coefficient r² ≥ 0.90,
 - a minimum of 3 data points, including the last measured data point and excluding C_{max}, are available for the regression.
 If these 2 criteria could not be met, the slope of the terminal elimination phase will be considered as not calculable and all the parameters derived from this value (AUC_{0-∞}, t_{1/2}, ...) will be reported as not calculable (NC).
- **t_{1/2}** will be calculated according to the following equation: t_{1/2} = ln(2)/ λ_z.
- **AUC₀₋₂₄** The area under the concentration vs. time curve from time zero (pre-dose) to 24 h post-dose will be calculated using a linear trapezoidal method.
- **AUC_{0-t}** The area under the concentration vs. time curve from time zero (pre-dose) to the time of last quantifiable concentration will be calculated using a linear trapezoidal method.
- **AUC_{0-∞}** The area under the serum drug concentration vs. time curve from time zero to infinity: [AUC_{0-∞} = AUC_{0-t} + (C_t/λ_z)], where C_t = the observed concentration of drug for the last sample on the PK profile in which drug was detected, and λ_z as defined above. The percentage of extrapolation of AUC_{0-∞} should normally not exceed 20% to consider the value as reliable.
- **fu** Fraction of unbound in plasma defined as the ratio of the unbound concentration over the total concentration
- **CL/F** The apparent oral clearance will be estimated, for the parent drug only, using the formula:

$$CL/F = \text{Dose} / AUC_{0-∞}$$
- **Vz/F** The apparent volume of distribution will be calculated for the parent drug only, based on the terminal elimination phase, as follows

$$Vd/F = CL/F / λ_z$$
- Parent to metabolite ratios will be calculated for C_{max} and AUC_{0-∞} as the ratio of the metabolite (C_{max} or AUC_{0-∞}) over the parent drug (C_{max} or AUC_{0-∞}).
- **A_{e,ur(t1-t2)}** Amount of DF 2577Y (or metabolites) excreted in urine over a fraction of time t1 to time t2 from :

$$Ae = \text{DF 2577Y (or metabolites) concentration} \times \text{Urinary volume of the fraction}$$
- **A_{e,ur(0-72)}** the cumulative amount excreted in urine from 0 to 72 h as the sum of all the amount excreted over each period of time
- **f_{e,ur (t1-t2)}** Percentage of the dose excreted in the urine for DF2577Y only, between time t1 and time t2 as (A_{e,ur(t1-t2)}/dose)×100
- **f_{e,ur (0-72)}** Total percentage of the dose excreted in the urine for DF 2577Y only, between 0 and 72 h as (A_{e,ur(0-72)}/dose)×100
- **CLR** Renal clearance determined as the ratio Ae₀₋₇₂/AUC₀₋₇₂ with t = 24 h post-dose and t_{last}
- **A_{e,f(t1-t2)}** Amount of DF 2577Y (or metabolites) excreted in feces over a fraction of time t1 to time t2 from :

$A_e = DF\ 2577Y$ (or metabolites) concentration \times feces weight

- $A_{e,f(0-72)}$ the cumulative amount excreted in feces from 0 to 72 h as the sum of all the amount excreted over each period of time
- $f_{e,f(t_1-t_2)}$ Percentage of the dose excreted in the feces for DF 2577Y only, between time t_1 and time t_2 as $(A_{e,f(t_1-t_2)}/dose) \times 100$
- $f_{e,f(0-72)}$ Total percentage of the dose excreted in the feces for DF 2577Y only, between 0 and 72 h as $(A_{e,f(0-72)}/dose) \times 100$

Individual derived PK parameters will be presented by dose level for each compound (parent and/or metabolites). Descriptive statistics of the PK parameters will be presented as N, mean, SD, standard error (SE), coefficient of variation (CV%), median, minimum (Min), maximum (Max) values, and geometric mean (GM).

Derivation of PK parameters will be carried out using WinNonlin® Professional software (Version Phoenix 6.4 – Pharsight Corporation – Mountain View, California – USA) using the methodology described above.

▪ Dose proportionality assessment:

For DF 2577Y bound and unbound and related metabolites, the hypothesis that C_{max} , $AUC_{0-\infty}$ are dose proportional will be formally tested using a power model approach. AUC and C_{max} values, for all dose levels, will be analyzed for dose proportionality using analysis of variance techniques.

Data will be fitted to the following model:

$$\log(AUC \text{ or } C_{max}) = \mu + [\beta \times \log(\text{Dose})]$$

This is usually referred to as a power model because after exponentiation:

$$AUC_{0-\infty} \text{ or } C_{max} = \alpha \times \text{Dose}^\beta$$

Prior to the analysis, the assumption of a linear relationship between the $\log AUC_{0-\infty}$ (C_{max}) and log-dose will be tested using analysis of variance by partitioning the sums of squares for treatments into those for linearity and departures from linearity. If the departures from linearity are significant then the hypothesis of dose proportionality is rejected and the power model analysis will not be performed.

In case, $AUC_{0-\infty}$ could not be considered as reliable in a majority of subjects (e.g. too large percentage of extrapolation, poor quality of k_e determination), dose proportionality assessment will be performed on AUC_{0-t} values.

The estimate obtained for β is a measure of dose proportionality. The estimate of β together with its 90% confidence interval (CI) (β_l , β_u) will be presented to quantify the degree of non-proportionality.

The dose proportionality will be confirmed if the 90% CI of β (β_l , β_u) is contained completely within the following critical region:

$$[\Theta_L; \Theta_H] = \left[1 + \frac{\log(0.8)}{\log(r)}; 1 + \frac{\log(1.25)}{\log(r)} \right]$$

where r , defined as the dose ratio, is equal to h/l , h being the highest dose and l the lowest dose.

Assessment of the dose proportionality will be performed on the complete dose range. In case of departures from linearity or of negative conclusion of dose proportionality on the complete dose, further investigation using the same methodology might be done on a restrained dose range.

For each day of PK assessment, the individual AUC and C_{max} values will be presented graphically by dose level. The mean AUC and C_{max} values along with the SD will also be displayed graphically by dose level.

The statistical package SAS® v.9.4 will be used to perform all statistical analyses.

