3.1.2. Secondary endpoints

Measurement of pharmacokinetics parameters: C_{max} , t_{max} , λ_z , $t_{1/2}$, AUC_{0-last} , AUC_{inf} , V_z/F , CL/F , Ae_{0-last} , CL_R , total amount in faeces, parent:metabolite(s) ratio.

Measurement of Cytokine Inflammation Markers [CXCL1(Gro alfa), CXCL2(Gro beta); CXCL5(ENA-78), CXCL6 (GCP-2), CXCL8 (IL-8)] in part B and Leukocyte subsets (CD11b and CD18) in part A, except for 1st cohort and part B.

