Vd/F The apparent volume of distribution based on the terminal elimination phase. The estimate does not account for the bioavailability (F, as a fraction of 1) and is therefore nominally divided by this value when drug is given via extravascular routes (DF 2577Y only in SAD part only).

$$Vd/F = Cl/F / ke$$

PTF The peak trough fluctuation will be calculated on Day 14 as the following ratio:

$$[(C_{ss, max} - C_{ss, trough})/C_{ss, av}]$$

where $C_{ss, trough}$ is the pre-dose concentration measured on the day of assessment.

In the MAD part, accumulation ratios will be calculated for C_{max} and AUC_{0-t} between Day 14 and Day 1 for each compound.

Parent to metabolite ratios will be calculated for C_{max} and all AUCs.

The following PK parameters of DF 2577Y (or related metabolites) will be derived from DF 2577Y (or related metabolites) urine concentrations for each:

Ae Amount of DF 2577Y (or related metabolites) measured in a given urine fraction:

$Ae = DF 2577Y$ (or related metabolites) concentration measured in the fraction \times Urinary volume of the fraction

fe Percentage of the dose excreted in the urine (DF 2577Y only) determined over various time intervals (24 h post-dose and t_{last} in SAD part; 12 and 24 h post-dose on Day 1 in MAD part).

Cl_R Renal clearance determined as the ratio Ae_{0-t}/AUC_{0-t} with $t = 24$ h post-dose and t_{last} in SAD part and $t = 12$ and 24 h post-dose on Day 1 in MAD part

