4.3 Pharmacokinetics and pharmacodynamics analyses

Criteria	Cmax (ng/mL); tmax (h); λZ ; $t_{1/2}(h)$; AUC ₀₋₂₄ (h×ng/mL); AUC _{0-t} (h×ng/mL); AUC _{0-∞} (h×ng/mL); fu VZ/F (DF2577Y only); CL/F (DF2577Y only); $A_{e,ur}$; $f_{e,ur}$ $A_{e,f}$; $f_{e,f}$ CLR; Parent:metabolite(s) ratio for Cmax and AUCs.
Information	Interim analyses will be performed after completion of each dose level, using anonymized data provided by the bioanalytical center Final PK analysis will be performed using validated bioanalytical data and actual PK blood sampling times of the part A of the study
Population	PKS
Statistical method	Descriptive statistics of concentrations and PK parameters Dose proportionality analysis using power model (section 3.3)
Title of tables	List of concentrations Descriptive statistics of concentrations List of PK parameters Descriptive statistics of PK parameters

Pharmacodynamic analysis: correlation between Cmax and pharmacodynamics criteria

Criteria	Pharmacokinetic criterion DF2577Y Cmax (ng/mL) Pharmacodynamic criteria Leukocyte markers: CD11b, CD18
Information	DF2577Y concentration assessed at D1 (pre-dose, T30min, T1h, T2h, T3h, T4h, T5h, T6h, T7h, T8h, T9h, T10h, T11, T12h, T16h), D2 (T24h, T36h, T40h), D3 (T48h, T60h) and D4 (T72h). Leukocytes markers not assessed for first cohort. Leukocytes markers assessed at D1 (Tcmax, Tcmax+3h, T12h), D2 (T24h), D3 (T48h) or D4 (T72h) (time determined after the results of the first dose administered).
Population	PKS
Statistical method	Time matched: D1 (Tcmax, Tcmax+3h, T12h), D2 (T24h), D3 (T48h) or D4 (T72h). The relationship between values of pharmacodynamic parameters time matched with DF2577Y (bound and unbound) plasma concentrations will be first evaluated by visual inspection of graphs relating pharmacodynamic parameters with DF2577Y (bound and unbound) plasma concentrations. In case of reliable relationships, basic models, such as Emax model, will be first developed. Then, the selected models will be optimized by testing covariate such as BMI, age, etc. Further model development might be done depending on the results of each modelling.
Title of tables	Cmax concentration vs CD11b for each time matched. Cmax concentration vs CD18 for each time matched.

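### SAP 3.3 names a parent to metabolite ratio but computes metabolite over parent, and it drops AUCs that the protocol asks for

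*SAP*

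**What the plan says.** Protocol 3.1.2 includes the "parent:metabolite(s) ratio" among the secondary pharmacokinetic endpoints, as does the protocol synopsis. Protocol 6.1 gives the derivation rule: "Parent to metabolite ratios will be calculated for C_{max} and all AUCs". It gives no formula. Protocol 6.2 lists the ratio under the same name for Part A and for Days 1 and 14 of Part B.

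The SAP uses the same name in its evaluation criteria (section 1), in the criteria row of its pharmacokinetic analysis table (4.3, "Parent:metabolite(s) ratio for Cmax and AUCs") and in its individual data listings (section 5).

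SAP 3.3 is the only place that states a calculation. It calls the quantity a parent to metabolite ratio, for Cmax and AUC0-∞, and then defines it "as the ratio of the metabolite" (Cmax or AUC0-∞) over the same parameter of the parent drug.

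**The concern.** The name and the formula in SAP 3.3 point in opposite directions, and the formula is the only one available to a programmer. If it is followed, a named secondary endpoint is reported upside down. A value of 0.1 read under its label says that the metabolite is ten times the parent, when the data say that it is a tenth. The ratio bears on the secondary objective about metabolite pathways, so its direction should not be in doubt.

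The sentence also narrows the endpoint. AUC0-∞ depends on the terminal slope, and SAP 3.3 reports it as not calculable when the slope fails its acceptance criteria. AUC0-24 and AUC0-t carry no such condition but are left out of the ratio.

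**Working it through.** There is no planned figure to reproduce, since the documents give no expected ratio. The check is a comparison of texts, followed by simple arithmetic on the consequence.

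**1. Direction.**

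| Place | Name | Formula |
|---|---|---|
| Protocol synopsis, 3.1.2, 6.1, 6.2 | parent to metabolite | none |
| SAP 1, 4.3, 5 | parent to metabolite | none |
| SAP 3.3 | parent to metabolite | metabolite / parent |

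SAP 3.1 says that its methods take account of those in the protocol, and no change to this endpoint is declared. The formula therefore cannot be read as a deliberate redefinition.

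**2. Size for one subject.** Let R = parent / metabolite. The SAP formula returns 1/R. For an assumed metabolite at 10% of parent, R = 1/0.10 = 10 and the SAP value is 0.1.

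For scale only, Protocol 1.2.1.3 puts parent above 66% of dog plasma radioactivity and one metabolite, M8, at 2 to 10%. Taking parent at 66%:

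- M8 at 10%: 66/10 = 6.6, against 10/66 = 0.15
- M8 at 2%: 66/2 = 33, against 2/66 = 0.03

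These are shares of radioactivity, not human Cmax or AUC ratios.

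**3. Whether the summaries can be inverted.** SAP 3.3 plans N, mean, SD, SE, CV%, median, minimum, maximum and geometric mean. Part A has six active subjects per cohort. Take six assumed values of R: 6.6, 10, 15, 20, 25, 33.

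| Statistic | From R | From 1/R | Inverse of the 1/R figure |
|---|---|---|---|
| Geometric mean | 15.93 | 0.0628 | 15.93 (exact) |
| Arithmetic mean | 109.6/6 = 18.27 | 0.0731 | 13.68 |
| Median | (15 + 20)/2 = 17.5 | (1/15 + 1/20)/2 = 0.0583 | 17.14 |
| SD | 9.80 | 0.0456 | no inverse relation |
| CV% | 53.7 | 62.3 | no inverse relation |

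The minimum and maximum invert and change places. The geometric mean inverts exactly. The median inverts only approximately when the number of subjects is even. The arithmetic mean, SD, SE and CV% have to be recomputed from individual values.

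**4. Which AUCs.** For Part A, Protocol 6.2 and SAP 3.3 both derive AUC0-24, AUC0-t and AUC0-∞, so all AUCs means these three. SAP 3.3 keeps one of them for the ratio. It reports AUC0-∞ as not calculable unless the terminal fit has r² of at least 0.90 and at least three points that exclude Cmax. For dose proportionality it falls back on AUC0-t when AUC0-∞ is unreliable in most subjects. It gives no fallback for the ratio. Cmax does not use the terminal slope, so the Cmax ratio remains available.

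**The case against.** The strongest reply is that this is a labelling slip with little consequence. SAP 3.3 states the numerator and denominator openly, so the direction is documented. Parent and metabolite concentrations and parameters are presented separately for each compound, so a reader can see which is larger. Individual ratios can be inverted, and the remaining summaries can be recomputed from the listings. All of this stands, and it limits the weight of the point. It does not remove the contradiction between the formula and the endpoint name.

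Three stronger readings are tempting but not supported:

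- **A table would carry the wrong title.** The phrase in SAP 4.3 is a criterion label. The table titles listed there refer only to concentrations and PK parameters in general. A parameter label may carry the phrase, but no title does.
- **The endpoint could be left empty.** Only the AUC part depends on the terminal slope. The documents also do not say which metabolites would lack a calculable AUC0-∞.
- **The comparison of human with animal metabolism would be reversed.** The ratio is a human figure. The animal metabolite data in Protocol 1.2.1.3 are percentages of radioactivity by matrix, so the documents contain no animal Cmax or AUC ratio to set against it.

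It can also be said that SAP 4.3 and section 5 already refer to AUCs in the plural, so the restriction may be another wording mismatch and not a decision. That is fair. The derivation text is still the narrower one, and it is what a programmer would follow.

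**Conclusion.** The point holds on the text. SAP 3.3 contradicts both itself and the protocol on the direction of a named secondary endpoint, and its derivation covers fewer AUCs than Protocol 6.1 asks for. If the sentence is programmed as written, each reported value is the reciprocal of the endpoint, and four of the planned summaries (arithmetic mean, SD, SE, CV%) cannot be recovered from the summary table alone.

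The 10 against 0.1 example rests on an assumed metabolite level, and the six-subject table on assumed values. Both show only how the reversal behaves. No exposure is misestimated. A missing AUC ratio is a possibility for subjects without a calculable AUC0-∞, not a prediction.

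The impact is confined to a descriptive secondary pharmacokinetic endpoint. The formal pharmacokinetic test concerns dose proportionality of Cmax and AUC, and neither the stopping rules (Protocol 3.5) nor the escalation criteria (Protocol 3.3.3.2) use this ratio.

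**What to change.** In SAP 3.3, define the ratio as parent divided by metabolite. Alternatively, keep the present formula, rename the quantity metabolite:parent in every SAP section, table and listing, and declare the change from the protocol. In either case, compute it for Cmax, AUC0-24, AUC0-t and AUC0-∞, so that an AUC ratio remains available when AUC0-∞ is not calculable.

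The cost is one line in the SAP and in the program, and no new data are needed. If outputs already exist, check which direction was programmed. Then correct either the label or the values, recomputing the arithmetic mean, SD, SE, CV% and median from the individual ratios.
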